4.2.1. Definition of estimands

Primary Estimands supporting the primary objective are defined as:

- Population: separate assessment for the following:
 - participants with CHB on stable nucleos(t)ide therapy
 - participants with CHB not currently on nucleos(t)ide therapy
- **Variable**: Sustained virologic response (SVR) for 24 weeks after the planned end of GSK3228836 treatment in the absence of rescue medication.
- **Treatments**: arms 1, 2, and 3. Estimation of the within-arm response rate. Note: arm 4 is described in Section 4.4.1
- **Intercurrent events**: use of rescue medication, and discontinuation of/interruption of/adherence to IP. The use of rescue medication has been incorporated into the definition of variable (composite strategy). Discontinuation of, interruption of, and adherence to IP not due to wide disruptive event will be ignored (treatment policy). Wide disruptive events

(such as COVID-19 pandemic) leading to discontinuation of, interruption of, and non-adherence to GSK3228836 will be handled assuming they had not happened (hypothetical strategy).

- **Population summary**: proportion of participants who achieve SVR for each treatment arm.

The primary estimands for each sub-population is the proportion of participants in each treatment arm 1, 2, and 3 who achieve SVR for 24 weeks after the planned end of GSK3228836 treatment in the absence of rescue medication regardless of completing IP, interruptions in IP or adherence to IP had they not been affected by wide disruptive events.

4.2.2. Main analytical approach

The participant population (on nucelos(t)ide treatment or not currently on nucleos(t)ide treatment) will not be included as a stratification factor in the analysis model, as each population will be analyzed separately.

A Bayesian hierarchical model will be fitted using MCMC methods, and will be used to estimate the posterior probability of sustained virologic response rate for each arm incorporating the baseline analysis stratification factors (Table 1) [Jones, 2011].

Model for each arm:

Number of responders
$$r_q \sim Binomial(n_q, p_q)$$
, $g = 1, 2, 3, 4$

$$\theta_g = logit(P_g) = log\left(\frac{P_g}{1 - P_g}\right) = \gamma_0 + \gamma_1 I_{\{B1+\}} + \gamma_2 I_{\{B2+\}} + \psi_g, \qquad g = 1, 2, 3, 4$$

Where $\gamma_0, \gamma_1, \gamma_2, \psi_g$ are all parameters. Thus,

$$\theta_1 = \, \gamma_0 + \, \psi_1$$

$$\theta_2 = \gamma_0 + \gamma_1 + \psi_2$$

$$\theta_3 = \gamma_0 + \gamma_2 + \psi_3$$

$$\theta_4 = \gamma_0 + \gamma_1 + \gamma_2 + \psi_4$$

Priors:

$$\gamma_k \sim Normal(0, 10^6), k = 0, 1, 2$$

$$\psi_g \sim Normal(0,\omega^2\,), g=1,2,3,4$$

$$\omega \sim Half - normal(1)$$

Where we define r_g as the number of SVR responders among n_g participants, p_g as SVR rate $\frac{r_g}{n_g}$, θ_g as the log odds of treatment response $\log(\frac{p_g}{1-p_g})$, index g=1,...,4 refers to the analysis stratum number, γ_k represent fixed effects of baseline analysis stratification factors (see below), and ψ_g denotes a random effect in analysis stratum g.

The four analysis strata and representation of the two baseline analysis stratification factors B_1 and B_2 in the model are shown in Table 1.

Stratum	B_1 : HBsAg ($I_{\{B1+\}}$)	B_2 : HBeAg $(I_{\{B2+\}})$
1: HBsAg ≤3 log IU/mL and Negative HBeAg	B₁- (< 3 log IU/mL) (0)	B ₂₋ (Negative) (0)
2: HBsAg >3 log IU/mL and Negative HBeAg	B ₁₊ (>3 log IU/mL) (1)	B ₂₋ (Negative) (0)
3: HBsAg ≤3 log IU/mL and Positive HBeAg	B₁- (< 3 log IU/mL) (0)	B ₂₊ (Positive) (1)
4: HBsAg >3 log IU/mL and Positive HBeAg	B ₁₊ (>3 log IU/mL) (1)	B ₂₊ (Positive) (1)

For each arm, the posterior distribution of SVR rate P(pg|data), g=1,2,3,4 will be derived for each analysis stratum using the model specified above.

$$P(p_1|data) = P(\frac{e^{\theta_1}}{1 + e^{\theta_1}}|data)$$

$$P(p_2|data) = P(\frac{e^{\theta_2}}{1 + e^{\theta_2}}|data)$$

$$P(p_3|data) = P(\frac{e^{\theta_3}}{1 + e^{\theta_3}}|data)$$

$$P(p_4|data) = P(\frac{e^{\theta_4}}{1 + e^{\theta_4}}|data)$$

The posterior distribution of the arm-level SVR rate will be derived using a mixture of the posterior distributions of SVR rate for each analysis stratum in that arm. The weights are proportional to the sample size of each analysis stratum in each arm.

$$P(p|data) = \sum_{g=1}^{4} w_g P(p_g|data)$$
, where $w_g = \frac{n_g}{\sum_{g=1}^{4} n_g}$

Posterior probability of SVR rate exceeding a range of clinically meaningful response rates, e.g., 10%, 15%, 20%, will be generated using the approach specified above for each arm.

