The posterior distribution of the arm-level SVR rate will be derived using a mixture of the posterior distributions of SVR rate for each stratum in that arm. The weights are proportional to the sample size of each stratum.

Posterior probability of sustained virologic response rate exceeding a range of clinically meaningful response rates will be generated using the approach specified above for each arm.

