Comparisons between arms will be made by calculating differences between the posterior distributions of the response rate in each arm which will be summarised to obtain posterior means and CIs. Samples from the posterior distribution of the response rates in each arm will also be used to obtain posterior probabilities of interest (e.g. Pr(Arm 1 - Arm 2 > -5% | Data)). The point estimates of differences in sustained virologic response rate with 95% credible intervals will be calculated for the treatment comparisons described in the estimands.

Posterior probability for the differences of following comparisons will also be reported;

- 1. Arm 1 vs. Arm 2
- 2. Arm 1 vs. Arm 3
- 3. Arm 2 vs. Arm 3

[figure not shown]
Regimen Selection Approach

If success criteria is met for more than one arm, regimen selection will be conducted. The non-inferiority (NI) decision rules for two-treatment comparison is Posterior Prob(less intensive arm SVR rate – more intensive arm SVR rate > -5%) > 65%. The arms are ordered in intensity from 1 (most intensive) to 4 (least intensive).

[figure not shown]
For each comparison, the posterior distribution of difference in SVR rate will be derived and the posterior probability (less intensive arm SVR rate - more intensive arm SVR rate > -5%) will be obtained based on the model described in Main analytical approach present under Section 4.3.1.2. If posterior probability is >65%, EoS NI rule is met.

If 2 arms meet the success rule, NI comparison between the 2 arms will be conducted. If the NI rule is met, then select the less intensive arm, otherwise select the more intensive arm.

If 3 arms meet the success rule, sequential two-treatment comparisons will be conducted for the 3 arms. The regimen selection follows the decision tree below.

If 4 arms meet the success rule, sequential two-treatment comparisons will be conducted for the 4 arms. The regimen selection follows the decision tree below.

Operating Characteristics for Regimen Selection

The Operating characteristics of regimen selection are summarized in Table 5 for a range of scenarios.

Table 5 Operating Characteristics for Regimen Selection

Arm 1 True rate	Arm 2 True rate	Arm 3 True rate	Arm 4 True rate	Prob of selecting arm 1	Prob of selecting arm 2	Prob of selecting arm 3	Prob of selecting arm 4	Prob of selecting none
30%	30%	30%	30%	16%	21%	28%	35%	0%
30%	30%	30%	25%	19%	26%	36%	19%	0%
30%	30%	25%	30%	21%	29%	11%	39%	0%
30%	25%	30%	30%	21%	7%	33%	39%	0%

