5. SAMPLE SIZE DETERMINATION

Approximately 440 participants are planned to be randomly assigned to study intervention.

For each population, there will be approximately 66 participants assigned in each of the first three arms. There will be approximately 22 participants assigned in the fourth arm.

It is assumed that the number of responders follows a Binomial distribution, with a weakly informative prior (Beta (0.5, 0.5)) for the true response rate. The precision for a range of response rates with 95% credible intervals are shown in Table 10.

Table 10 95% Credible Interval of Response Rate by Sample Size

Sample size per arm	Number of responders	Response rate	95% credible interval*
22	2	9%	1% – 23%
	3	14%	3% - 30%
	4	18%	5% - 36%
	5	23%	8% - 41%
	6	27%	11% - 46%
66	6	9%	3% - 17%
	9	14%	6% - 23%
	12	18%	10% - 28%
	15	23%	13% - 33%
	18	27%	17% - 38%

^{*95%} highest posterior density interval

The lower bounds of 95% credible intervals will exclude the historical placebo response rate of 3% if observed response rate is greater than or equal to 14% in arms 1-3 or 18% in arm 4.

The posterior probabilities that the true sustained virologic response rate is greater than a range of response rates will be calculated from the implied Beta posterior, given the actual number of responders observed.

The operating characteristics based on at least 75% posterior confidence that the true rate exceeds a threshold of interest, are shown in Table 11, for various sample sizes, and true cure rates. The operating characteristics shown are based on a Bayesian model without consideration of baseline analysis stratification factors and expected to be similar to operating characteristics from the hierarchical model defined in Section 4.2.2.

Table 11 End of Study Operating Characteristics by Sample Size

Criterion	Sample Minimum size per number (%) arm of		Probabili	ty of Meeting Assun	Criterion Und	er Various
		responders required to meet Criterion	True Resp Rate=5%	True Resp Rate=20%	True Resp Rate=25%	True Resp Rate=30%
Probability (true	22	5 (23%)	0%	46%	68%	84%
response	44	9 (20%)	0%	53%	81%	91%
rate>15%)>75%	66	12 (18%)	0%	69%	93%	99%
	88	16 (18%)	0%	71%	95%	100%
Probability (true	22	6 (27%)	0%	27%	48%	69%
response	44	11 (25%)	0%	25%	56%	81%
rate>20%)>75%	66	16 (24%)	0%	23%	60%	88%
	88	21 (24%)	0%	22%	64%	92%
Probability (true response rate>25%)>75%	22	7 (32%)	0%	13%	30%	51%
	44	13 (30%)	0%	9%	29%	58%
	66	19 (29%)	0%	6%	28%	63%
	88	25 (28%)	0%	4%	27%	67%

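### As written, the arm-level SVR posterior is a mixture of stratum posteriors, not the posterior of the arm's rate, so the primary intervals, threshold probabilities and non-inferiority results are wrong

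*SAP*

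**What the plan says.** The estimand in SAP Section 4.2.1 is the "proportion of participants who achieve SVR for each treatment arm". SAP Section 4.2.2 fits a Bayesian logistic model to each arm over four strata (HBsAg low or high, HBeAg negative or positive) and obtains a posterior for each stratum's SVR rate. The arm-level posterior "will be derived using a mixture of the posterior distributions of SVR rate for each analysis stratum in that arm". The formula that follows matches the words: P(p|data) is set equal to the sum of w_g·P(p_g|data), which is a weighted sum of distributions. On the weights: "The weights are proportional to the sample size of each analysis stratum in each arm". Protocol Section 9.4.3 has the same definition, "using a mixture of the posterior distributions of SVR rate for each stratum in that arm".

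The probabilities of exceeding 10%, 15% or 20% come from this distribution. SAP Section 4.3.1.2 carries it into the arm contrasts: "Comparisons between arms will be made by calculating differences between the posterior distributions of the response rate in each arm". Samples from the same arm posteriors feed the non-inferiority (NI) rule for regimen selection, with a margin of -5 points and a required posterior probability above 65%. SAP Section 5 bases its design figures on an unstratified Beta-Binomial model, and these are "expected to be similar to operating characteristics from the hierarchical model defined in Section 4.2.2".

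**The concern.** With fixed weights w_g = n_g/n, the arm's response rate is p = Σ w_g p_g. Its posterior comes from forming that sum within each draw. A mixture of the stratum posteriors describes a different quantity: pick a stratum with probability w_g and report its rate. The mixture has the right mean, but it adds the spread between strata and does not average the uncertainty within them.

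The trial estimates rates and has no hypothesis test. The credible intervals and threshold probabilities are therefore its primary outputs, alongside the point estimate. If the mixture is programmed, an effective arm can look unconvincing because its strata differ or are small. Two arms with identical data can fail NI against each other. The operating characteristics that supported 66 per arm would not be delivered.

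**Working it through.** **Inputs.** From the documents: 66 participants in each of arms 1-3; a Beta(0.5, 0.5) prior for the design figures; a 75% success criterion; γ_k ~ N(0, 10⁶), ψ_g ~ N(0, ω²), ω ~ Half-normal(1). Assumed, because the documents give neither stratum sizes nor stratum rates: set A has sizes 16/26/4/20 and set B has 16/30/6/14 (strata 1 to 4).

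**1. The plan's own figures.** With 12/66 the pooled posterior gives P(p>15%) = 0.77, and with 11/66 it gives 0.66, so 12 is the minimum. P(X≥12 | 66, 0.20) = 69.1%. For the 20% threshold, 16/66 gives 0.81 and 15/66 gives 0.72, so 16 is the minimum. P(X≥16 | 66, 0.30) = 87.7%. Both match SAP Table 11 (69% and 88%). All ten intervals in SAP Table 10 also reproduce.

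**2. Variance by formula.**
- Mixture: Var = Σ w_g Var(p_g) + Σ w_g (m_g - m)², where m_g is the stratum mean and m the arm mean.
- Arm rate: Var(Σ w_g p_g), about p(1-p)/n when the strata share one rate.

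In that equal-rate case, Σ (n_g/n) Var(p_g) ≈ k·p(1-p)/n, where k is the effective number of parameters. Here k lies between 3 (interaction shrunk to zero) and 4 (strata fitted separately). Even if the observed stratum rates are all equal, the mixture SD is about √3 = 1.7 to √4 = 2.0 times too large. Differences between strata add to that.

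**3. Example data, model fitted by MCMC with the stated priors.**

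| Responders by stratum | Weighted average: 95% interval, probability | Mixture: 95% interval, probability | SAP Table 10 |
|---|---|---|---|
| 8/16, 7/26, 1/4, 2/20 (18/66) | 18%-38%, P(>20%) = 0.93 | 3%-66%, P(>20%) = 0.60-0.61 | 17%-38% |
| 3/16, 6/30, 1/6, 2/14 (12/66) | 10%-28%, P(>15%) = 0.74 | 4%-37%, P(>15%) = 0.62 | 10%-28% |
| 7/16, 4/30, 1/6, 0/14 (12/66) | 10.5%-27%, P(>15%) = 0.77-0.78 | 0%-61%, P(>15%) = 0.41 | 10%-28% |
| 3 each of 17/17/16/16 (12/66) | 10%-28% | 5%-38% | 10%-28% |

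The width ratios run from 33/18 = 1.8 (rows 2 and 4) through 63/20 = 3.2 (row 1) to 61/16.5 = 3.7 (row 3).

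**4. More data does not cure it when strata differ.** With ten times the 18/66 data, the weighted average narrows to 24%-31%, while the mixture still spans 7%-55% with P(>20%) = 0.68-0.69. That is close to the share of participants in strata above 20%: (16+26+4)/66 = 0.70.

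**5. Operating characteristics** (set A: 800 simulated arms per scenario; set B: 250).

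| Scenario and criterion | Stated | Weighted average (A; B) | Mixture (A; B) |
|---|---|---|---|
| 20% in every stratum, P(>15%)>75% | 69% | 63%; 65% | 23%; 22% |
| Unequal strata, arm about 20%, same criterion | 69% | B 68% | 2.5%; 2% |
| 30% in every stratum, P(>20%)>75% | 88% | 88%; 89% | 52%; 51% |
| Unequal strata, arm about 30%, same criterion | 88% | B 90% | 18%; 14% |

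The unequal rates were 40/19/20/5% and 50/30/25/15% in A, and 45/15/15/4% and 60/24/25/10% in B. In B at about 20%, the lower 95% bound exceeds the 3% historical placebo rate in 42% (equal) or 7% (unequal) of arms under the mixture, against about 100% under the weighted average.

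**6. Non-inferiority.** For two arms with identical 18/66 data, P(difference > -5%) is 0.76 from the weighted average (rule met) and 0.58-0.59 from the mixture (rule fails). With ten times the data the mixture still gives 0.64, against 0.98. For truly equal arms the rule is met 58%-68% of the time with the weighted average and 22%-41% with the mixture (set B).

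**The case against.** The strongest reply is that this is loose notation and not what will be programmed. The SAP uses P(·|data) freely, and even writes p_g as the observed fraction r_g/n_g, so the sum might be shorthand for averaging draws. Section 5 expects agreement with a pooled model, and only the weighted average gives that. SAP Table 5 also fits a pooled calculation if success there means the 20% criterion. For true rates 25/25/25/30%, the chance that no arm succeeds is 0.40³ × 0.31 = 2%, as printed. The intent may well be right. But words and formula agree with each other in the SAP, the protocol repeats the words, and nothing elsewhere overrides them. A programmer following the plan would produce the mixture.

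Some limits do stand:
- Posterior means are identical, so a mean-based point estimate and mean difference are unaffected.
- If all strata truly share one rate, the mixture does converge as n grows; it is too wide only at finite n.
- NI verdicts change in some data sets, not all. With 16 against 12 responders both versions fail (0.43-0.44 and 0.48-0.51).
- The 75% criterion is a design criterion, not a test of the primary objective.
- NI is run only if more than one arm succeeds.
- The expected similarity in Section 5 becomes roughly true once the formula is corrected.

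**Conclusion.** The concern holds. As written, both documents define the wrong distribution for the arm-level SVR rate. Intervals are about 1.8 to 3.7 times too wide in the examples. The chance of meeting the success criteria falls from the stated 69% and 88% to 22-23% and 51-52% with equal stratum rates, and to about 2% and 14-18% with unequal ones. The NI rule can fail for arms with identical data, and failure then selects the more intensive arm.

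These sizes rest on assumed stratum sizes and rates. The direction does not: equal strata with near-equal response rates still give intervals 1.8 times too wide. If the code already averages within draws, the results will be right, but the plan still misstates the primary analysis. It must be corrected before final results are produced.

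**What to change.** In SAP Section 4.2.2, replace the mixture sentence and formula with this: in each MCMC draw s, compute p(s) = Σ w_g p_g(s), with w_g = n_g/Σ n_g; the draws p(s) are the posterior of the arm-level SVR rate. State that these draws are used for the credible interval, the threshold probabilities, the arm differences in Sections 4.3.1.2 and 4.4.1.1, and the NI probability. Align protocol Section 9.4.3, and check the final code against the new definition.

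The analytic cost is one formula and one line of code, with no new data. There is a procedural cost. A protocol change needs an amendment with ethics approval; until then the correction can be recorded in SAP Section 4.8 as a change from the protocol. Sponsor staff named in the blinding plan are unblinded at the third interim, and SAP amendment 01 already contains analyses requested there. The correction should therefore be dated and should explain that it follows from the estimand and the design figures, not from observed results.

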4.2.2.1. Visit windowing and multiple measurements at one analysis timepoint

Visit windowing for the primary endpoint will be applied as specified in Table 2 and Table 3 and the windowed results will be used to determine the primary endpoint of SVR. Unscheduled assessments will be included in the analysis window. No imputation of missing data will be performed prior to visit windowing.

If there are multiple values within an analysis window the following rules will be applied:

For the End of '836 Treatment Analysis Timepoint:

1. The latest available assessment in the window will be selected.

For Post '836 Treatment Analysis Timepoints:

- 1. Worst non-missing value in the analysis window will be selected, if values are the same then the value closest to target day will be selected. If there are multiple values equidistant from the target day, the earliest will be selected. If all values within an analysis window are missing, then the result is missing for the analysis window.
- 2. Worst value is defined in the order of: highest actual value, then <LLOQ, and then TND.

Table 2 Primary endpoint analysis windows for Arms 1, 2 and 4

Analysis	Parameter	Target	Analysis	Window	Analysis	Protocol
Set / Domain	(if applicable)	Study Day	Beginning Timepoint	Ending Timepoint	Timepoint	Visit
Efficacy	HBsAg and HBV DNA	162	148	182	End of '836 Treatment	Week 24
		218	183	238	Post '836 treatment Week 8	Off treatment Week 8
		274	239	294	Post '836 treatment Week 16	Off treatment Week 16
		330	295	350	Post '836 treatment Week 24	Off treatment Week 24

Table 3 Primary endpoint analysis windows for Arm 3

Analysis	Analysis Parameter		Analysi	s Window	Analysis	Protocol
Set / Domain	(if applicable)	Study Day	Beginning Timepoint	Ending Timepoint	Timepoint	Visit
Efficacy	HBsAg and HBV DNA	78	64	98	End of '836 Treatment	Week 12
		134	99	154	Post '836 treatment Week 8	Week 20
		190	155	210	Post '836 treatment Week 16	Off treatment Week 4
		246	211	266	Post '836 treatment Week 24	Off treatment Week 12

The primary analysis will be based on planned end of treatment regardless of whether a patient discontinued treatment early.

For the second supplementary estimand described in Section 4.2.4.2, SVR will be measured from actual rather than planned end of treatment and the analysis windows should be amended accordingly. For this estimand, the date of last dose should be treated as the reference date and the rules in Table 4 should be used to determine the endpoint of SVR.

Table 4	Supplementary	endpoint anal	lysis windows Arms	s 1, 2, 3 and 4
---------	---------------	---------------	--------------------	-----------------

Analysis Parameter (if		Reference	Analysi	is Window	Analysis Timepoint
Set / Domain	applicable)	day	Beginning Timepoint	Ending Timepoint	
Efficacy	HBsAg and HBV DNA	Reference date	Reference date - 14	Reference date + 20	End of '836 Treatment
		Reference date + 56	Reference date + 21	Reference date + 76	Post '836 treatment Week 8
		Reference date + 112	Reference date + 77	Reference date + 132	Post '836 treatment Week 16
		Reference date + 168	Reference date + 133	Reference date + 188	Post '836 treatment Week 24

